C-1728 30610 Treatment and Response Form	Every 2 cycles during protocol treatment (including the non-protocol cycle of chemo, if applicable).
C-660 Solid Tumor Evaluation Form	
Report CT scan reports	
C-1729 Adverse Event Form	Every cycle during protocol treatment
C-1742 Confirmation of Lost to Follow-up Form	Follow form directions.
C-1730 Follow-up and Response Form	After the end of protocol treatment submit every 3 months for 2 years, then every 6 months for 3 years, then every year for an additional 5 years until progression. After progression submit only the C-1730 every 6 months to report survival, new malignancy, and non-protocol treatment data. Report new malignancy on the C-1001.
C-660 Solid Tumor Evaluation Form	
Report CT scan reports	
C-1001 New Malignancy Form	

This study will use NCI Common Terminology Criteria for Adverse Events (CTCAE) version 3.0 for routine toxicity reporting on study forms. However, CTCAE version 5.0 will be used for **serious** AE reporting through CTEP-AERS as of April 1, 2018; see [Section 16.0](#).

* Use CALGB Remarks Addenda (C-260) if additional comments are necessary or additional writing space is needed.

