6.3.1 Plasma Collection for both Correlative Science Studies (see [Section 10.1](#))

For patients who consent to participate, 20 ml of whole blood (in two 10 ml purple top tubes) will be collected at the following time points:

- Baseline (before treatment initiation)
- Day 1 of Cycles 2, 3 and 4 (pre-chemotherapy),
- At first follow-up after completion of all protocol treatment,
- At each post-treatment follow-up visit (Follow-up is every 3 months for 2 years, then every 6 months for 3 years, and then yearly. Note: If follow-up is completed more often than required a plasma sample is preferred by is not required.)
- At the time of recurrence.

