* Pre-registration labs may be used for day 1 of cycle 1 tests if obtained within 14 days prior to day 1 of Cycle 1. For subsequent cycles labs may be obtained within 48 hours prior to day of treatment. Patients receiving treatment on a Monday may have labs obtained within 72 hours.

** Weight must be recorded weekly during thoracic radiotherapy

*** At least every 3 months for 2 years, then every 6 months for 3 years, then every year for an additional 5 years until disease progression. After progression, follow every 6 months for survival and new malignancy.

† The dose of chemotherapy need not be changed unless the calculated dose changes by ≥ 10%.

A See [Section 13.5.3](#) for CT instructions. Note that a CT scan made as part of the PET-CT is acceptable if it meets all the criteria in Section 13.5.3. Any CT scan that does not meet these requirements must be repeated.

B Obtain on days 1 and 8 of each cycle.

C Obtain MRI or CT of brain prior to initiating prophylactic cranial irradiation.

D Obtain 6 and 12 months from the start of treatment, then as clinically indicated.

Ψ For those patients who consent to participate in the substudies.

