In addition to analyzing the small cell lung cancer specific biomarkers as described above, we will also include two additional groups of proteins. First, we will assess factors that we have already established to be modulated by radiotherapy or endothelial damage, including VEGF, soluble VEGFR-2, and E-selectin [53-55]. The second set of factors will be proangiogenic cytokines that may contribute to resistance by promoting the proliferation and survival of tumor endothelial cells. First, several selected proangiogenic cytokines

known to play a role in angiogenesis in lung cancer, including VEGF, basic fibroblast growth factor (bFGF), transforming growth factor α (TGF- α), and interleukin-8 (IL-8).

Objectives: The objectives of the correlative studies for small cell specific circulating markers are:

1. To investigate the value of the published markers specific to small cell lung cancer in the large phase III clinical study setting. We will analyze the baseline biomarker profile, changes in the profile during treatment at the time of recurrence to correlate with the response rate, progression free survival, and overall survival of these patients.
2. To compare the differences in the biomarker profile between the two treatment arms.

Hypotheses

1. Circulating biomarkers may have prognostic or predictive value of small cell lung cancer.
2. The differences in circulating biomarkers between the two treatment arms may reveal information correlating with efficacy of treatments.

Method for the ELISA Assay

ELISA is a standard laboratory analytical method for protein quantification in the plasma or serum (R&D Systems, Minneapolis, MN). This assay requires a significant volume of sample (100-200 μ l) for each biomarker. The ELISA assay has high sensitivity and high precision, and thus has been the standard assay of cytokine measurement.

10.1.3 ProGRP as a Marker to Monitor the Response to Therapy and for the Prediction of Relapse Following Therapy

The goal of this correlative study is to evaluate the performance of proGRP as a biomarker in SCLC lung cancer. In addition, this study will provide an opportunity to better understand the role proGRP to monitor the response to therapy and the relapse following therapy.

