There have been many publications over the years showing the clinical utility of proGRP as a marker for SCLC. Some important reviews of the literature (96-98) have demonstrated the proGRP was the best tumor marker in his evaluation for patients with SCLC. In addition, the National Academy of Clinical Biochemists Practice Guidelines and Recommendations for the Use of Tumor Markers in Lung cancer recognize the clinical use of proGRP in the differential diagnosis of lung masses and in the monitoring of therapy response and detection of recurrent disease (Stieber et al, manuscript in review, Clin Chem.) From the multiple reports, it is clear that proGRP is a valuable tumor marker for SCLC, but it has not been validated in a prospective study.

Objectives: The objectives of this correlative study are:

Primary:

- 1) To evaluate the correspondence between increases in plasma ProGRP concentrations and disease progression/recurrence.

Secondary:

- 1) To evaluate the potential for plasma ProGRP concentrations at baseline, after each cycle of chemotherapy and at first evaluation following completion of chemotherapy to predict PFS and OS.
- 2) To evaluate the correspondence between longitudinal decreases in plasma ProGRP concentrations and clinical response.

Exploratory:

- 1) To evaluate novel biomarkers for their ability to improve correspondence and prediction of response to therapy in patients with SCLC. This may involve the use of multiple biomarkers, including ProGRP, in conjunction with the biomarkers specific for small cell lung cancer being studied by [REDACTED]

Hypotheses

- 1) ProGRP will have a relatively high sensitivity, specificity and early recognition of relapse in patients with SCLC. An increase in proGRP level may be detected approximately a month prior to clinical evidence of relapse
- 2) The majority of patients under treatment will show decreased levels of ProGRP, particularly those with objective responses. NSE and proGRP together may be a combination of biomarkers that most accurately predicts response to therapy.

Methods

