The goal of this correlative study is to obtain information on the clinical value of ProGRP in the US to support an FDA submission and to provide information on its clinical utility to the medical professionals responsible for treating patients with SCLC.

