Most studies of proGRP have reported that approximately 70-80% of patients have increased levels of proGRP in their serum or plasma. The primary endpoint examines the correlation of increases in the plasma proGRP levels with changes in disease status. This strategy is based on the analyses performed for tumor markers used for monitoring and approved by the FDA, such as CA19-9, CA15-3, CA125 and CEA. Changes above a cutoff are compared for to clinical evaluation of stable disease vs. progression. In the secondary studies, the correlation of decreases in proGRP level will be compared to stable disease vs. regression and/or remission designations. The data is analyzed as concordance of 2 X 2 table of clinical outcome vs. a defined change in cutoff levels. For proGRP, 3 levels will be evaluated initially a) the percent increase that is 2.5 times the assay's observed total percent coefficient of variation (CV), b) a percent change that is 2.5 times the assay and biological variation, and c) a change of >25% based on changes used with other cancer biomarkers. The change in disease state is evaluated per sequential pair and per patient. Secondary analyses can determine whether a different cutoff functions better than these 3 cutoffs. Individual patients will be evaluated by following their sequential proGRP values and their clinical status via tables and graphs.

Based on the numbers of patients and samples sufficient for these evaluations for other monitoring biomarkers as submitted to and approved by the FDA, it is recommended that between 150 and 200 patients be enrolled in this study. A sample size of approximately 150 and 200 patients will provide a sufficient number of evaluable patients with 95% confidence and 80% to 90% statistical power for evaluating the association of the change in ProGRP assay values and change in disease status.

For the primary study and the secondary studies of the relationship of proGRP levels at baseline and at each round of chemotherapy and at the end of therapy will be analyzed as defined above.

Analytic Methods

All data from eligible patients with evaluable measures of the biomarker of interest will be included in final analysis. A 2-sided significance level of 0.05 will be used for all tests.

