To assess the correspondence between increases in plasma ProGRP and disease progression or recurrence, patients will be considered evaluable if they have at least five blood draws, one at baseline and the remaining draws at 3, 6, 9 and 12 months, respectively with the corresponding scans at those time points. Patients with CR, PR, and SD will be grouped together as non-progressive disease for the statistical analysis. Since each patient contributes a unique set of visit pairs to the data, this must be controlled by using techniques developed for generalized linear models. GENMOD procedure in SAS will be used to obtain the estimates of the concordances. The relationship between the concordance estimate C and the parameter estimate b is given by $C = (1 + e^{-b})^{-1}$. 95% confidence limits will be determined for all concordance proportion.

To evaluate the ability of ProGRP at baseline, after each cycle of chemotherapy and at first evaluation post-treatment, patients will be grouped into two different groups based on their ProGRP concentrations. At each of those intervals, they will be grouped as negative if (ProGRP \leq 50 pg/mL) or as positive if (ProGRP $>$ 50 pg/mL). In addition, changes in ProGRP concentrations starting at baseline and after the first or second dose of chemotherapy will also be explored. The log-rank test will be used to determine if the PFS for patients with positive values (or changes) are different from the negatives.

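### The ProGRP concordance analysis requires draws and scans through month 12, but scheduled scans stop at progression, so entry depends on the outcome and most first-year failures are lost

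*Combined protocol and SAP*

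**What the plan says.** Section 10.1.3 gives the primary objective of the ProGRP substudy: "To evaluate the correspondence between increases in plasma ProGRP concentrations and disease progression/recurrence". It also says that the goal is to "obtain information on the clinical value of ProGRP in the US to support an FDA submission".

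Under Analytic Methods, Section 15.6 restricts that analysis to patients who are "evaluable if they have at least five blood draws, one at baseline and the remaining draws at 3, 6, 9 and 12 months", with a scan required at each of the same times. No exception is made for patients who progress or die earlier. The rule belongs to the concordance analysis only; the log-rank comparison of PFS by ProGRP level in the next paragraph does not carry it.

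The follow-up schedule works differently:

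- Section 7.0, footnote to the post-treatment column (which includes chest CT): visits run until progression, and then "After progression, follow every 6 months for survival and new malignancy".
- Section 6.1: "After progression submit only the C-1730 every 6 months to report survival, new malignancy, and non-protocol treatment data". The tumor evaluation form and CT reports are no longer requested.
- Section 6.3.1: plasma is drawn at every follow-up visit and also "At the time of recurrence".

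For the planned unit of analysis, Section 15.6 states: "The change in disease state is evaluated per sequential pair and per patient".

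**The concern.** Concordance between marker rise and progression can be learned only from visits where progression is and is not found. A patient whose progression is found at or before the 9-month scan has no scheduled 12-month scan, and a patient who dies before month 12 cannot have one. The recurrence sample collected from such patients does not make up for the missing time points. Being evaluable is thus largely a matter of being progression-free at the 9-month scan, which is the outcome under study.

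Followed as written, the estimate would describe patients who reach about 12 months, although Section 10.1.3 hypothesizes early recognition of relapse and intends the result for a regulatory submission.

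A secondary, exploratory point has the same root. Section 10.1.2 plans to use "changes in the profile during treatment at the time of recurrence to correlate with the response rate, progression free survival, and overall survival". The power text for that substudy in Section 15.6 likewise lists change at recurrence among the measures related to response, FFS and OS. That value exists only after an FFS event, so it cannot predict FFS from randomization. Analytic Methods refers instead to change during treatment, so the places disagree.

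**Working it through.** **The plan's own figure.** Section 15.6 recommends 150 to 200 patients for 80% to 90% power, but gives no effect size, progression rate or evaluable fraction. It acknowledges that evaluable patients are what count, but not how many are expected to be lost. The figure cannot be reproduced.

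**Inputs for the size of the loss**

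- 2-year FFS of 40%: the planning value at the biomarker mean in the power text for the first and second correlative substudies (Section 15.6), borrowed here.
- Exponential FFS: an assumption. The protocol states this shape only for OS (Section 15.3).
- Months counted from randomization: an assumption. Section 15.6 gives no time origin.
- Perfect compliance with draws and scans otherwise.

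**Formula.** S(t) = 0.40^(t/24).

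- S(9) = 0.40^(9/24) = 0.709, so 29.1% have failed by month 9.
- S(12) = 0.40^(12/24) = 0.632, so 36.8% have failed by month 12.

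The loss is 29.1% if every failure between months 9 and 12 is a progression first seen on the 12-month scan (these patients qualify), and 36.8% if none is.

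- Of 150 patients: 0.291 × 150 = 43.6 to 0.368 × 150 = 55.1.
- Of 200 patients: 58.2 to 73.5.
- Share of failures by 24 months: 0.291/0.60 = 48.5% to 0.368/0.60 = 61.3%.
- S(60) = 0.101. Share of failures by 60 months: 0.291/0.899 = 32.4% to 0.368/0.899 = 40.9%.
- Share of first-year failures, even at the smaller loss: 0.291/0.368 = 79%. About 12 to 15 of 55 to 74 first-year failures could enter.

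**Sensitivity to the borrowed FFS**

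| 2-year FFS | S(9) | S(12) | Patients lost |
|---|---|---|---|
| 30% | 0.637 | 0.548 | 36.3-45.2% |
| 40% | 0.709 | 0.632 | 29.1-36.8% |
| 50% | 0.771 | 0.707 | 22.9-29.3% |

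**Sensitivity to time origin.** If the months run from about 3 months later (end of treatment), the relevant values are S(12) = 0.632 and S(15) = 0.564, and the loss is 37-44%.

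**Sensitivity to curve shape.** With Weibull shape 0.8 to 2, 2-year FFS 30% to 50% and either time origin, and counting only failures up to the 9-month scan as lost, 58-89% of first-year failures are excluded. The excluded share of failures by 24 months ranges from 19% to 71%.

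**Enrollment if the rule were kept.** To leave 150 to 200 evaluable at the smaller loss: 150/0.709 gives 212 and 200/0.709 gives 283.

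**The case against.** The strongest reply is that many progressions remain. The rule asks for at least five draws, so any progression found at or after month 12 in a patient with the required pairs is usable. On the base case, 59-68% of failures by 5 years are not removed. This stands: the claim that most are lost is robust only for the first year.

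The magnitude rests on a borrowed FFS value, an assumed curve and an unstated time origin. FFS also counts deaths without progression, so failure counts overstate progressions. Section 6.3.1 does not say that draws stop at progression, and unscheduled scans could rescue some patients. These points widen the range but do not remove the dependence on outcome.

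The text also leans the other way in places: Section 15.6 includes all data from eligible patients with evaluable measures, and expects each patient to contribute its own set of visit pairs. A general sentence does not override a specific evaluability rule, but the tension supports clarifying the text.

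Selection by time of progression distorts concordance only if ProGRP behaves differently in early progressors, and the documents do not show that. Restricted generalizability and lost progression data are shown; a biased estimate in a known direction is not.

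On the secondary point, the tests are labeled exploratory and the list may merely describe types of variable. The label waives multiplicity adjustment; it does not make a post-event value a valid predictor of that event.

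**Conclusion.** The concern holds. The evaluability rule for the substudy's primary analysis selects on the outcome it studies, and the schedule does not supply the scans the rule demands once a patient has progressed. The expected loss is about 29-37% of patients in the base case, and 23-45% as 2-year FFS moves between 50% and 30%, subject to the exponential and time-origin assumptions. Most first-year failures are lost under every setting tried. The direction and size of any bias in concordance are unknown. This is an optional companion study, and the trial's primary OS comparison is unaffected. The change is worth making because the analysis is the substudy's primary one and the correction is cheap.

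**What to change.** Amend Analytic Methods in Section 15.6:

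1. Define a patient as evaluable with a baseline draw and at least one later draw that has a paired disease assessment.
2. Use all consecutive draw-scan pairs up to and including progression in the planned GENMOD analysis.
3. Report the already planned per-patient analysis alongside the per-pair one. The number of pairs will depend on outcome, and modeling repeated pairs does not by itself resolve that.
4. Keep the five-draw set as a sensitivity analysis, and state the time origin of months 3 to 12.

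For the secondary point, reconcile the Section 10.1.2 objectives with the power text and Analytic Methods of Section 15.6. Do not use change at recurrence to predict response, FFS or OS from randomization; if it is of interest, relate it to survival timed from recurrence. Analyze earlier on-treatment or post-treatment changes from a landmark at the draw concerned.

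The cost is SAP wording, with no new visits or samples beyond those in Sections 6.3.1 and 7.0. One reconciliation is needed: the opening of Section 15.6 lists draws only at baseline, day 21, first follow-up and recurrence, which is fewer than Section 6.3.1 schedules and would not supply the 3- to 12-month series.

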15.1.3 Secondary Endpoint

Secondary endpoints will include complete and partial response rates, failure-free survival, local tumor progression according to RECIST criteria, and rates of distant metastases and intracranial metastases. Failure free survival is the time from randomization to death of all causes or disease progression, whichever comes first. Second primary tumors will not be viewed as disease progression.

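### ProGRP groups formed at post-baseline draws can appear to predict PFS because patients who have already progressed by the draw are not excluded

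*Combined protocol and SAP*

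**What the plan says.** Section 15.6 (Analytic Methods) sets up the ProGRP prediction analysis at several times: "To evaluate the ability of ProGRP at baseline, after each cycle of chemotherapy and at first evaluation post-treatment". At each one, patients above 50 pg/mL are positive and the rest negative. Change groups are added: "changes in ProGRP concentrations starting at baseline and after the first or second dose of chemotherapy will also be explored". The comparison is one sentence: "The log-rank test will be used to determine if the PFS for patients with positive values (or changes) are different from the negatives".

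The analysis set for all of Section 15.6 is broad: "All data from eligible patients with evaluable measures of the biomarker of interest will be included in final analysis". The test level is also common: "A 2-sided significance level of 0.05 will be used for all tests". On size, the section says "it is recommended that between 150 and 200 patients be enrolled in this study".

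PFS is not defined anywhere. The nearest endpoint is in Section 15.1.3: "Failure free survival is the time from randomization to death of all causes or disease progression". The rule requiring five draws belongs to the concordance analysis, not to this log-rank test.

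Section 6.3.1 schedules plasma at baseline, on day 1 of cycles 2, 3 and 4, at the first follow-up after treatment, at each later follow-up visit, and at recurrence. Section 10.1.3 reports that ProGRP generally moves upward in progressive disease.

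**The concern.** The groups are formed weeks or months after randomization, but nothing says that a patient must still be at risk of the event when grouped. If a patient has already progressed, or is found to have progressed at the visit where blood is drawn, the event time is at or before the classification. ProGRP tends to rise with progression, so these patients tend to land in the positive group. The log-rank test then counts their events as evidence that a positive value foretells progression.

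That is detection of existing disease, which the primary concordance objective of the ProGRP substudy already addresses. Objective 2.2.8 asks something different: whether the value predicts PFS and OS. At stake is a false claim of prediction in a secondary analysis of a substudy that Section 10.1.3 says should support a regulatory submission.

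**Working it through.** **The plan's own figure.** Section 15.6 claims 80% to 90% power with 150 to 200 patients. This concerns ProGRP change against change in disease status. It comes without effect size, concordance, event count or group split, so it cannot be reproduced. No figure is given for the PFS log-rank test.

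**Inputs from the documents.**
- 2-year FFS of 40% (Section 15.6, first substudy).
- Three-week cycles, so day 1 of cycles 2, 3 and 4 falls at about weeks 3, 6 and 9. Four cycles last 12 weeks and follow-up is 3-monthly, which puts the first post-treatment draw at about weeks 12 to 25.
- Accrual of 6 years plus 2.5 years of follow-up (Section 15.3), giving censoring uniform from 30 to 102 months.
- About 70% to 80% of patients have raised ProGRP (Section 15.6). This anchors positivity in patients who have progressed.

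**Assumptions not in the documents.** Exponential PFS; positivity of 75% in patients who failed before the draw and 30% in the others (varied over 70-80% and 20-40%); 25%, 50% or 100% of pre-draw failures having a sample; ProGRP unrelated to PFS after the draw.

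**Share failed before the draw.** Hazard = -ln(0.40)/24 = 0.0382 per month. Share failed = 1 - exp(-0.0382 × months). This gives 2.6% at week 3, 5.1% at week 6, 7.6% at week 9, 10.0% at week 12, 13.1% at week 16 and 19.7% at week 25.

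**Simulated type I error.** Two-sided 0.05 log-rank from randomization, pre-draw failures kept, 75% versus 30% positive, 2,000 trials per cell. Each cell shows 150 / 200 analysed patients.

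| Draw | 25% sampled | 50% sampled | 100% sampled |
|---|---|---|---|
| Week 3 | 5.2% / 5.8% | 6.0% / 5.6% | 7.4% / 7.6% |
| Week 6 | 5.5% / 5.5% | 7.4% / 8.0% | 11.5% / 11.5% |
| Week 9 | 6.4% / 5.8% | 9.2% / 10.3% | 17.5% / 23.2% |
| Week 12 | 7.6% / 7.6% | 10.8% / 14.7% | 24.0% / 30.0% |
| Week 16 | 8.4% / 10.2% | 14.8% / 16.8% | 35.6% / 46.8% |
| Week 25 | 13.0% / 13.2% | 29.4% / 34.9% | 60.4% / 73.5% |

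The table counts 150 to 200 as patients with a sample. If they are counted as enrolled, the range for weeks 12 to 25 is about 7% to 72%, or about 11% to 31% with half sampled. With half sampled, the mean hazard ratio is about 1.14 at week 12 and 1.30 at week 25, although the true value is 1. Over the wider positivity ranges, the first post-treatment draw runs from 6% to 94%.

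**Hand check of one cell** (week 25, half sampled, n = 150, about 134 events).
- Pre-draw failures analysed: 16.4, of whom 16.4 × 0.75 = 12.3 are positive.
- Positives at the start: (12.3 + 133.6 × 0.30)/150 = 0.349, falling to 0.30 by the draw, average about 0.325. Expected positive events before the draw: 16.4 × 0.325 = 5.3. Excess: 12.3 - 5.3 = 7.0.
- Variance: 16.4 × 0.325 × 0.675 + 117.6 × 0.30 × 0.70 = 3.6 + 24.7 = 28.3; square root 5.32.
- Shift: 7.0/5.32 = 1.31. Rejection: P(Z > 1.96 - 1.31) = P(Z > 0.65), about 26%. The simulation gave 29.4%.

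**With pre-draw failures removed,** type I error is 4.0% to 6.4% and the mean hazard ratio 1.00 to 1.04 in every setting, so the test is nominal within simulation error.

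**The case against.** The strongest reply is that the schedule already restricts the problem. On-treatment draws are tied to day 1 of a cycle. Section 14.1 continues treatment until progression and removes patients with rapid progression. Section 13.0 re-evaluates every 6 weeks, so no scheduled reassessment precedes the week 3 draw. After progression, Section 7.0 moves patients to 6-monthly follow-up for survival and new malignancy. The 10% to 20% failure share also includes deaths, and the dead cannot be sampled. A constant hazard may overstate early failure when the planning response rate is 80%.

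Much of this stands. It makes the upper ends of the ranges unlikely and the inflation at cycles 2 to 4 often small. But none of these rules is an analysis exclusion. Section 7.0 schedules a chest CT at post-treatment follow-up and Section 6.3.1 schedules plasma there, so progression found at the classifying visit is a plausible route in.

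A reader might infer several stronger things that the documents do not support:
- That the plan deliberately keeps progressed patients, or that progression certainly creates the association at every draw. The plan is silent on the risk set, and the number of progressed patients sampled is unknown.
- That OS is distorted in the same way. A sampled patient cannot have died before the draw.
- That patients missing a sample because they failed earlier add bias. Leaving them out acts as a landmark.
- That the regulatory case collapses. Section 15.6 rests that strategy on the concordance analysis; prediction of PFS is secondary, and the change groups are exploratory.

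**Conclusion.** The concern holds in a limited form. Followed as written, the PFS comparison for post-baseline ProGRP groups can include patients whose event is at or before classification, and the direction of the resulting bias favours a finding of prediction.

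It is material mainly at the first post-treatment evaluation: about 7% to 72% type I error if a quarter to all pre-draw failures are sampled, and about 11% to 31% if half are. At the cycle 2 to 4 draws it is about 5% to 11% if up to half are sampled, and reaches about 20% at cycle 4 only if all are. These sizes rest on assumed exponential PFS, assumed positivity and assumed sampling fractions. The existence of the gap does not.

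Baseline groups, the concordance analysis and the trial's primary OS comparison are unaffected.

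**What to change.** Amend Section 15.6 as follows.

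1. Define PFS for the ProGRP analyses, including its events and time origin.
2. For each post-baseline ProGRP time point and for the change groups, include in the PFS log-rank test only patients alive and progression-free at the draw. Exclude progression documented at or before that visit. Count time from the draw, or use ProGRP as a time-dependent covariate. For change groups, the draw is the later of the two.
3. For OS, require only that the patient is alive at the draw, and count time from the draw.
4. Apply the same at-risk rule to the Section 15.6 Cox models relating on-treatment marker change to FFS.
5. Keep the analysis from randomization for the baseline value.
6. Report the number excluded at each time point.

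Excluding patients who have already progressed is what removes the bias. If the draw time were the same for everyone, moving the clock would leave the log-rank test unchanged once they are out. Counting from the draw is still cleaner because the timing of the first follow-up visit varies.

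The cost is SAP wording and no new data collection, since draw dates and progression dates are already recorded. Each landmark has fewer patients and events: up to about 20% fewer patients at the latest draw if all early failures had been sampled, and fewer lost otherwise.
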